#### MD part

1. Pan-retinal photo coagulation treated PDR patients with either no or inactive retinal neovascularization per investigator judgement in the study eye
2. Male or female patients of age  $\geq 18$  years
3. Presence of significant DMI: large foveal avascular zone defined as those with  $\geq 0.5\text{mm}^2$  area in superficial vascular complex (SVC) present on optical coherence tomography angiography. If FAZ is  $< 0.5\text{mm}^2$  then enlarged peri-foveal inter-capillary space in at least 1 quadrant will be sufficient.
4. HbA1c of  $\leq 12.0\%$
5. If both eyes are eligible, the investigator may select either eye to be the study eye.
6. Best-corrected VA  $\leq 85$  letters (20/20) or worse for MD
7. Women of childbearing potential (WOCBP) and men able to father a child must be ready and able to use two methods of contraception with at least one of them being a highly effective methods of birth control per ICH M3 (R2) that result in a low failure rate of less than 1% per year when used consistently and correctly. A list of contraception methods meeting these criteria is provided in the patient information in Section [4.2.2.3](#)

8. Signed and dated written informed consent in accordance with ICH GCP and local legislation prior to admission to the trial
9. Signed and dated written informed consent for aqueous sampling (optional)

 A woman is considered of childbearing potential (WOCBP), i.e. fertile, following menarche and until becoming post-menopausal unless permanently sterile. Permanent sterilisation methods include hysterectomy, bilateral salpingectomy and bilateral oophorectomy. Tubal ligation is NOT a method of permanent sterilisation. A postmenopausal state is defined as no menses for 2 years without an alternative medical cause. A high follicle stimulating hormone (FSH) level in the postmenopausal range may be used to confirm a post-menopausal state in women not using hormonal contraception or hormonal replacement therapy. However, in the absence of 2 years of menorrhoea, a single FSH measurement is sufficient.

### 3.3.3 Exclusion criteria

Patients will not be allowed to participate, if any of the following general criteria apply:

#### SRD part

1. Patients receiving IVT injections for active DME (anti-VEGF, steroids) and macular laser in the study eye in the previous 3 months prior to enrolment
2. Patients receiving anti-VEGF IVT injections for active PDR in the study eye in the previous 3 months prior to enrolment
3. Current or planned use of medications known to be toxic to the retina, lens or optic nerve (e.g. desferoximine, chloroquine/hydrochloroquine, chlorpromazine, phenothiazines, tamoxifen, nicotinic acid, and ethambutol)
4. Additional eye disease in the study eye that could compromise best corrected VA (BCVA) with visual field loss, uncontrolled glaucoma (IOP>24), age related macular degeneration, history of ischemic optic neuropathy or retinal vascular occlusion, symptomatic vitreomacular traction, or genetic disorders such as retinitis pigmentosa; history of high myopia > 8 diopters in the study eye. Anterior segment and vitreous abnormalities in the study eye that would preclude adequate observation with SD-OCT
5. Any intraocular surgery in the study eye within 3 months prior to screening
6. Aphakia or total absence of the posterior capsule. Yttrium aluminium garnet (YAG) laser capsulotomy in the study eye if performed less than 3 months prior to enrolment
7. Patients not expected to comply with the protocol requirements or not expected to complete the trial as scheduled (e.g. chronic alcohol or drug abuse or any other condition that, in the investigator's opinion, makes the patient an unreliable trial participant)
8. Previous participation in this trial or in other trials with IVT injections administered within 3 months.
9. Significant disease or other medical conditions\* (as determined by medical history, examination and clinical investigations at screening) that may, in the opinion of the investigator result in any of the following:
  - a. Put the patient at risk because of participation in the study
  - b. Influence the results of the study
  - c. Cause concern regarding the patient's ability to participate in the study
10. Known hypersensitivity to any of the ingredients used in the investigational medicinal product (IMP) formulation, or any of the medications used
11. Active intraocular inflammation in the study eye
12. Active infectious conjunctivitis in either eye

13. Women who are pregnant, nursing, or who plan to become pregnant while in the trial

\*e.g. cardiac (including tachycardia), gastro-intestinal, hepatic, renal, metabolic, dermatologic, neurological, haematological, oncological and psychiatric. Patients with malignancy for which the patient has undergone resection, radiation or chemotherapy within past 5 years. Patients with treated basal cell carcinoma or fully cured squamous cell carcinoma are allowed.

MD part

1. DME, defined as a CST  $\geq 305\mu\text{m}$  for men and  $\geq 290\mu\text{m}$  women measured with Optovue OCT in the study eye
2. Patients receiving IVT injections for active DME (anti-VEGF, steroids) and macular laser in the study eye in the previous 3 months prior to enrolment
3. Patients receiving anti-VEGF IVT injections for active PDR in the study eye in the previous 3 months prior to enrolment
4. Heavily lasered macula in the study eye per investigator's judgement
5. History of vitrectomy in the study eye
6. Epiretinal membrane with extended foveal contour distortion in the study eye per investigator's judgement
7. Current or planned use of medications known to be toxic to the retina, lens or optic nerve (e.g. desferoximine, chloroquine/hydrochloroquine, chlorpromazine, phenothiazines, tamoxifen, nicotinic acid, and ethambutol)
8. Additional eye disease in the study eye that could compromise best corrected VA (BCVA) with visual field loss, uncontrolled glaucoma (IOP>24), age related macular degeneration history of ischemic optic neuropathy or retinal vascular occlusion, symptomatic vitreomacular traction, or genetic disorders such as retinitis pigmentosa; history of high myopia > 8 diopters in the study eye. Anterior segment and vitreous abnormalities in the study eye that would preclude adequate observation with SD-OCT
9. Any intraocular surgery in the study eye within 3 months prior to screening
10. Aphakia or total absence of the posterior capsule. Yttrium aluminium garnet (YAG) laser capsulotomy in the study eye if performed less than 3 months prior to enrolment
11. Patients not expected to comply with the protocol requirements or not expected to complete the trial as scheduled (e.g. chronic alcohol or drug abuse or any other condition that, in the investigator's opinion, makes the patient an unreliable trial participant)
12. Previous participation in this trial or in other trials with IVT injections within 3 months
13. Significant disease or other medical conditions\* (as determined by medical history, examination and clinical investigations at screening) that may, in the opinion of the investigator result in any of the following:
  - a. Put the patient at risk because of participation in the study
  - b. Influence the results of the study
  - c. Cause concern regarding the patient's ability to participate in the study
14. Known hypersensitivity to any of the ingredients used in the IMP formulation, or any of the medications used
15. Active intraocular inflammation in the study eye
16. Active infectious conjunctivitis in either eye

17. Women who are pregnant, nursing, or who plan to become pregnant while in the trial

\*e.g. cardiac (including tachycardia), gastro-intestinal, hepatic, renal, metabolic, dermatologic, neurological, haematological, oncological and psychiatric. Patients with malignancy for which the patient has undergone resection, radiation or chemotherapy within past 5 years. Patients with treated basal cell carcinoma or fully cured squamous cell carcinoma are allowed.

For study restrictions, refer to Section [4.2.2](#).

### 3.3.4 Withdrawal of patients from treatment or assessments

Patients may discontinue trial treatment or withdraw consent to trial participation as a whole ('withdrawal of consent') with very different implications; please see Sections 3.3.4.1 and [3.3.4.2](#).

Every effort should be made to keep the patients in the trial: if possible, on treatment, or at least to collect important trial data.

Measures to control the withdrawal rate include careful patient selection, appropriate explanation of the trial requirements and procedures prior to first administration of trial medication, as well as the explanation of the consequences of withdrawal.

The decision to withdraw from trial treatment or from the whole trial as well as the reason must be documented in the patient files and Case Report Form (CRF).

#### 3.3.4.1 Withdrawal from trial treatment

An individual patient will be withdrawn from trial treatment if:

1. The patient wants to withdraw from trial treatment, without the need to justify the decision
2. The patient has repeatedly shown to be non-compliant with important trial procedures and, in the opinion of both, the investigator and sponsor representative, is not willing or able to adhere to the trial requirements in the future
3. The patient needs to take concomitant medication that interferes with the investigational medicinal product or other trial treatment
4. The patient can no longer receive trial treatment for medical reasons (such as surgery, adverse events [AEs], other diseases or pregnancy)
5. An AE or clinically significant laboratory change or abnormality occurs that the investigator judge to warranting discontinuation of treatment.

Even if the trial treatment is discontinued (MD part), the patient remains in the trial and, given his/her agreement, will undergo the procedures and follow up as outlined in the [Flow Chart II](#) and Section [6.2.3](#).

### 3.3.4.2 Withdrawal of consent to trial participation

Patients may withdraw their consent to trial participation at any time without the need to justify the decision.

If a patient wants to withdraw consent, the investigator should be involved in the discussion with the patient and explain the difference between trial treatment discontinuation and withdrawal of consent to trial participation, as well as explain the options for continued follow up after trial treatment discontinuation, please see Section [3.3.4.1](#).

### 3.3.4.3 Discontinuation of the trial by the sponsor

Boehringer Ingelheim reserves the right to discontinue the trial overall or at a particular trial site at any time for any of the following reasons:

1. Failure to meet expected enrolment goals overall or at a particular trial site
2. Emergence of any efficacy/safety information invalidating the earlier positive benefit-risk assessment that could significantly affect the continuation of the trial
3. Deviation from GCP, the CTP, or the contract impairing the appropriate conduct of the trial.

For the following scenario further enrolment and entering into the trial will be interrupted by the sponsor once the sponsor becomes aware (i.e. stopping rule):

- A single serious adverse reaction (i.e. a single serious adverse event) or two severe adverse reactions in two different patients (regardless of the system organ class) confirmed by both the investigator and sponsor as having a reasonable causal relationship to the IMP administration.

The investigator / trial site will be reimbursed for reasonable expenses incurred in case of trial termination (except in case of the third reason).

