In addition a Safety Monitoring Committee (SMC) will be established to review individual and aggregated safety data at regular intervals to determine the safety profile and risk/benefit ratio and decide on the next dose level and the next cohort size, or the appropriacy of further enrolment (see section [8.7](#)).

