If DLEs are observed in the first two consecutive patients of a previously untested dose level, subsequent enrolment to that cohort will be stopped.

The maximum feasible dose (MFD) is considered as reached if at least 6 patients have been evaluated at a dose level which is the model's recommendation for the next dose cohort. Note the MFD will likely be the highest feasible dose, [REDACTED], rather than the highest tolerable dose in strict sense. The MD part of the study would only start if the highest dose ([REDACTED]) is tolerated.

- After the DLE period (7 days after drug administration) is over for the last patient in the SRD part, all available trial data will be analyzed and a decision is made whether to proceed to the MD part or not. Before starting the MD part, regulatory authorities and institutional review boards (IRBs) / independent ethics committees (IECs) will be informed of the internal results of the SRD part.

[figure not shown]

Figure 3.1: 1 Schematic representation of the dose escalation process in the SRD part of the trial

MD part:

The MD part will consist of one dose cohort (N=20 on dose + 10 sham injection). The highest dose [REDACTED] if established as safe and tolerable during the SRD part will be used in the MD part after the SRD part has been completed. Patients that had received a dose in the SRD part of the trial will not be included. Patients will be randomized to receive either active treatment or sham injection.

In the MD cohort, patients will receive three consecutive doses/sham injection over a 3-month period (dosing every 4 weeks). The SMC will meet regularly to review the safety data.

In all patients included in the MD part of the trial, safety and early biological response will be studied up to 98 days after the last injection.

[figure not shown]

Figure 3.1: 2                      Schematic representation of the dosing in the MD part of the trial

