## **6.2.2 Treatment period(s)**

For the SRD part, masking is not required for the IVT injection preparation or administration. For the MD part, IVT injection will be prepared by the unmasked pharmacist (qualified person). For the MD part, an unmasked injector with no other involvement in the trial will administer either active or sham injection according to the treatment assigned by IRT. IVT injections must be carried out according to medical standards and applicable guidelines by a qualified physician experienced in administering IVT injections and will be done as part of drug administration visit procedures (Visit 2 for SRD part and Visits 2, 3 and 4 for MD part) after the other ophthalmologic assessments in the [Flow Chart I](#) and [Flow Chart II](#) have been performed (please see Section [4.1](#) for details).

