## **8. INFORMED CONSENT, TRIAL RECORDS, DATA PROTECTION, PUBLICATION POLICY, AND ADMINISTRATIVE STRUCTURE**

The trial will be carried out in compliance with the protocol, the ethical principles laid down in the Declaration of Helsinki, in accordance with the ICH Harmonized Guideline for Good Clinical Practice (GCP), relevant BI SOPs, the EU regulation 536/2014, and other relevant regulations. Investigators and site staff must adhere to these principles.

Standard medical care (prophylactic, diagnostic, and therapeutic procedures) remains the responsibility of the patient's treating physician.

The investigator will inform the sponsor immediately of any urgent safety measures taken to protect the trial patients against any immediate hazard, as well as of any serious breaches of the protocol or of ICH GCP.

The Boehringer Ingelheim transparency and publication policy can be found on the following web page: [trials.boehringer-ingelheim.com](https://trials.boehringer-ingelheim.com). The rights of the investigator and of the sponsor with regard to publication of the results of this trial are described in the investigator contract. As a general rule, no trial results should be published prior to archiving of the CTR.

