## 8.7 ADMINISTRATIVE STRUCTURE OF THE TRIAL

The trial is sponsored by Boehringer Ingelheim (BI).

A Coordinating Investigator is responsible to coordinate investigators at the different sites participating in this trial. Tasks and responsibilities are defined in a contract.

An extended SMC will be established for both SRD and MD parts. The SMC shall operate under the principles specified in the SMC charter. The primary responsibility of the SMC is to ensure and protect the safety and well-being of the patients participating in the trial. The primary objectives of the SMC are to make a joint decision on dose escalation in the SRD part and on the transfer to the MD part after the SRD part has been completed.

The SMC will decide on the next dose level to be investigated based on occurrence of DLEs (see section [5.2.1](#)) and on additional information (systemic pharmacokinetics [PK] and patient profiles).

During the trial the SMC will monitor the trial for possible harmful effects of the test treatment, make an assessment as to the conduct of the trial, evaluate the accrued data in order to recommend whether the trial should continue as planned, continue with modification or stop the trial (e.g. for safety concerns or ethical reasons).

In its assessment and recommendations the SMC should always consider trial integrity/conduct issues (e.g. accrual, withdrawal rates, important protocol violations, relevant quality findings and non-compliances, missing data and censoring) and also consider factors external to the trial when relevant new information becomes available, such as scientific or therapeutic developments that may have an impact on the safety and well-being of the patients or on the ethics of the trial.

The SMC is a multidisciplinary group composed of the co-ordinating investigator, participating investigators (as deemed necessary) with treated patients in the cohort that will

be evaluated in the meeting (SRD part only), members of the BI trial team and two experts independent from the BI trial / project team in the field of ophthalmology. The SMC members have been selected for their expertise in these areas, their knowledge of the management of patients with DMI and their experience in clinical trials and SMC activities. Details of the SMC responsibilities and procedures are described in the SMC charter.

Relevant documentation on the participating (Principal) Investigators (e.g. their curricula vitae) will be filed in the ISF.

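### The stopping rule halts new entry only; in the three-injection MD part it sets no default hold on the pending second and third injections and no deadline for a decision.

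*Protocol*

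**What the plan says.** The rule is in protocol Section 3.3.4.3. It is triggered by one serious reaction, or by severe reactions in two different patients, that investigator and sponsor both confirm as reasonably related to administration of the product. The stated action is that "further enrolment and entering into the trial will be interrupted by the sponsor once the sponsor becomes aware (i.e. stopping rule". The trigger is not limited to the SRD or the MD part, and injections already scheduled are not mentioned.

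Dosing differs between the parts. Section 6.2.2 places injections at "Visit 2 for SRD part and Visits 2, 3 and 4 for MD part"; Flow Chart II puts the MD injections on Days 1, 29 and 57.

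The other relevant provisions are:

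- Section 1.4.2.4: the SMC reviews individual and aggregated safety data, assesses risk and benefit, and is to "decide on the next dose level and the next cohort size, or the appropriacy of further enrolment".
- Section 3.1, MD part: "The SMC will meet regularly to review the safety data". No interval is given.
- Section 8.7: the SMC may "recommend whether the trial should continue as planned, continue with modification or stop the trial". It adds: "Details of the SMC responsibilities and procedures are described in the SMC charter".
- Section 3.3.4.1: "An individual patient will be withdrawn from trial treatment if" one of five conditions applies, including an adverse event that the investigator thinks warrants it.
- Section 3.3.4.3 also lets the sponsor discontinue the trial on new safety information.
- Section 8 requires investigators to tell the sponsor of "urgent safety measures taken to protect the trial patients against any immediate hazard".
- Section 5.2.7.2.2: SAEs and AESIs reach the sponsor within 24 hours.
- Section 8.6 defines a temporary halt but does not tie it to this trigger.

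The SAP adds no rule on holding doses.

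**The concern.** The rule's wording fits a single-dose design, where stopping entry stops exposure. In a repeat-dose cohort it protects by default only people who have not yet entered. Randomised patients, due the same product at the same dose within four weeks, depend on someone choosing to act, with no stated deadline. Once the last patient, including any replacement, has entered, the rule has nothing left to interrupt, although up to two injections per patient may still be due over the next 8 weeks.

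This is the first repeat dosing in humans. Prior human exposure was 12 patients given single doses (Section 1.2). Some monkeys showed intraocular inflammation, which resolved (Table 1.4.2:1). The sentinel approach is described for the SRD part only (Section 1.4.2.4). The residual effect period is unknown (Section 1.2.1), and the top dose is predicted to stay above the minimum efficacious vitreous concentration for 116 days (Section 4.1.2). An injection at four weeks therefore adds to drug that is predicted to be still active.

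**Working it through.** The plan gives no figure to reproduce; the point rests on the text. The arithmetic below only sizes what the rule leaves out.

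**Share of planned injections (Section 3.1: 20 active, 10 sham, three injections each).**
- Active: 20 × 3 = 60 injections, of which 20 × 2 = 40 (67%) are second or third.
- Both arms: 30 × 3 = 90 procedures, of which 30 × 2 = 60 are second or third.

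**Pending injections when the rule fires.** The documents give no accrual duration, so 13, 26 and 52 weeks are assumed. The simulation used 4,000 runs per setting: 30 patients entering uniformly at random, 2:1 allocation in blocks of three, injections on Days 1, 29 and 57, and a trigger after a randomly chosen active injection. The affected patient's own remaining doses are excluded.

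| Assumed accrual | 13 weeks | 26 weeks | 52 weeks |
|---|---|---|---|
| Pending active injections | 13.0 | 7.5 | 3.8 |
| Pending active plus sham | 20.0 | 11.7 | 6.2 |
| Patients concerned, both arms | 13.4 | 7.8 | 4.1 |
| Trigger at or after last entry | 34% | 18% | 12% |
| Pending active, 7-day confirmation lag | 12.7 | 7.4 | 3.9 |
| At or after last entry, 7-day lag | 41% | 22% | 13% |

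Other seeds change the zero-lag active counts by about 0.2 and the last-entry percentages by about 2 points.

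**Chance that one serious related reaction fires the rule, 20 active patients.**
- Assumed risk 1% per patient: 1 − 0.99^20 = 18.2%.
- Assumed risk 5% per patient: 1 − 0.95^20 = 64.2%.
- Procedural reactions only, at the 0.1% ceiling in Section 1.4.2.2: 1 − 0.999^20 = 2.0% if per patient, or 1 − 0.999^60 = 5.8% if per injection.

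**What the SRD part rules out.** With 0 of 12 patients having a related event, the one-sided 95% upper bound is 1 − 0.05^(1/12) = 22.1% per patient. This covers any related event, not only serious ones, after single doses pooled over three levels.

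**Cost of a hold, both arms, no lag, accrual 13 / 26 / 52 weeks.**
- A 7-day hold moves 3.4 / 2.0 / 1.0 injections, of which 1.9 / 1.1 / 0.6 move by more than 3 days.
- A 14-day hold moves 6.7 / 3.9 / 2.0 injections, of which 5.3 / 3.1 / 1.6 move by more than 3 days.

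**Effect on Visit 5.** SAP Section 6.7 counts visit windows from the first treatment day, so Visit 5 stays at Day 85. A third injection on time leaves 85 − 57 = 28 days; 7 days late leaves 85 − 64 = 21; 14 days late leaves 85 − 71 = 14.

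**The case against.** The strongest reply is that the protocol sends SMC procedures to a charter we have not seen. Whether a related serious event convenes the committee, how fast, and whether dosing pauses meanwhile may all be settled there. This stands: only the protocol's silence is shown, not a gap in the trial's whole safety governance.

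Second, randomised patients are not unprotected. The SMC covers both parts, includes two independent ophthalmology experts and can recommend modification or a stop. The sponsor handles the data open label (Section 4.1.6.1), must itself confirm the trigger and hears of SAEs within 24 hours. A four-week interval usually leaves time to act. All of this is true, and nothing in the protocol says that dosing must continue. But each route is discretionary; none is tied to the trigger or to the next injection visit, and Section 3.3.4.1 concerns the individual patient only.

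Third, case-by-case judgement is a legitimate design choice, since one procedure-related event could otherwise freeze both arms. That is a real cost, but a small one if the hold lasts only until the SMC decides.

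Fourth, the counts depend on assumed accrual and vary more than threefold. They are injections outside the rule, not injections that would necessarily be given. The 5% risk has no support in the documents. These limits are accepted; the textual point needs none of the figures.

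**Conclusion.** The concern holds as a limited, inexpensive safety improvement that should be made. The protocol's stopping rule contains no automatic hold on MD dosing, does not say that its trigger convenes the SMC, and requires no decision before the next injection. If the rule fires, roughly 4 to 13 active injections in other randomised patients (6 to 20 with sham) fall outside it under accrual of 52 down to 13 weeks. In roughly 12% to 34% of such cases it would have no entry left to stop.

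Confidence is medium, because the charter may already supply the hold and the dosing interval usually allows time to act. SAP Section 6.1 records recruitment as completed, so the change matters for any injections still pending and as wording for later repeat-dose trials.

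**What to change.** Reword Section 3.3.4.3 so that, when the existing trigger is met:

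- further entry and all further MD injections, active and sham alike so that masking is kept, are held until an ad hoc SMC review under Section 8.7 decides to resume, modify or stop;
- follow-up visits and safety assessments continue during the hold;
- an injection delayed beyond the ±3-day window is either given late or omitted, under one stated rule for both arms.

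Mirror this in the SMC charter, or cite the charter if it already contains such a rule.

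Trigger, committee and reporting route stay the same. The costs are an occasional ad hoc meeting, sometimes for a procedure-related event, and a few moved or omitted injections. A late third injection shortens the interval to Visit 5, a secondary FAZ time point, and an omitted one breaks the three-dose regimen for that patient.
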